However, since a large proportion of the population has GERD, it is neither practical nor cost-effective to screen everyone with GERD with traditional upper endoscopy. Therefore, risk-stratification tools¹⁸ and alternate screening methods to EGD with both endoscopic and non-endoscopic approaches have been explored (Figure 2). Of the endoscopic approaches, Transnasal Endoscopy (TNE) is as sensitive as EGD for BE diagnosis, well tolerated, and less expensive.¹⁵⁻¹⁸ TNE uses a small caliber scope that is inserted into the nares after application of local anesthetic, and can be performed without sedation. Of the non-endoscopic screening techniques, the most studied is an ingestible sponge attached to a string, Cytosponge. Cytosponge is a minimally invasive, sponge-based technique for sampling the esophageal mucosa. It is an abrasive sponge encapsulated in a gelatin coating, which is attached to a string. After ingestion, the capsule dissolves upon exposure to gastric secretions. It is then withdrawn through the hiatus and distal esophagus and out of the mouth by the string, sampling cardiac and esophageal epithelium.

The resulting sample is immunostained for markers, which have been sensitive and specific for the presence of BE. Cytosponge has also been shown to have good acceptability and tolerance by patients.^{19,20}

These alternate screening modalities, while demonstrated to be effective, have not been implemented in clinical practice. There are prior studies comparing the clinical effectiveness and patient acceptability measures between EGD and TNE,^{21,22} and more recently EGD and Cytosponge.¹⁹ To date, however, no study has simultaneously evaluated all three available modalities. Given that we have more available screening tools, it is vital to understand patient acceptability in utilizing these new modalities. Therefore, the goal of the study is to compare patient acceptance and preference between three screening modalities for BE: traditional upper endoscopy (EGD), Transnasal Endoscopy (TNE), and Cytosponge.

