9 STATISTICAL CONSIDERATIONS

9.1 Statistical Plan & Sample Size Calculation

The acceptability of each screening modality will be assessed with the Impact of Events Scale (IES) scores, and the intrusiveness and avoidance subscales. We plan to recruit 40 subjects for the study.

Since the same subject will undergo treatment with each of the screening modalities, we anticipate that the scores generated will be correlated. We assume each pair of scores will have the same correlation. For the planned analysis, each IES score will be classified as low or high. High score will be defined as total IES score >38 .²⁵ A low score will be defined as a total IES score less than or equal to 38.

To compute power, for each of the three devices we specified the proportion of high scores as well as the correlation between observations within a subject. Estimating that 1% of the subjects undergoing sedated EGD group, 5% of those undergoing Cytosponge,²⁵ and 20% of those undergoing TNE will experience a high IES score, using a correlation of 0.3, and a sample size of 40, we specified a trivariate Binomial distribution. Random data were generated from such a distribution and Fishers Exact Test was computed from the data. This was done 10,000 times. The percentage of the 10,000 trials in which the Fishers Exact Test p-value was less than 0.05 provided our power estimate of 80% for a sample size of 40.

We will compare the median IES score for each modality using Kruskal-Wallis testing as well comparing the proportion of subjects with high IES scores for each modality using Pearson's chi-square testing. For the secondary objectives:

- **Secondary objective 1:** Median VAS score will be compared between the three modalities using Kruskal-Wallis testing
- **Secondary objective 2:** The proportion of subjects willing to repeat each test will be computed.
- **Secondary objective 3:** Subjects' preferred screening modality ranked highest will be measured as proportions. The proportion of the highest ranked screening modality will be computed.
- **Secondary objective 4:** Bivariate and multinomial logistic regression analyses will be used to identify factors such as patient discomfort, sex, and EGD indication influencing screening preference among the three modalities.

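### Section 9.1 plans only three-group global tests, so a significant result cannot say which modality differs; the stated 80% is omnibus power for the high-IES proportion and rests on the assumed 20% TNE rate

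*Combined protocol and SAP*

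**What the plan says.** Section 2 gives the purpose: "the goal of the study is to compare patient acceptance and preference between three screening modalities for BE". Section 3.1 words the primary objective more loosely, as assessing acceptance of each modality by IES. Section 5.1 restates it as a comparison, and for that reason has patients undergo all three procedures.

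For the primary outcome, Section 9.1 says: "We will compare the median IES score for each modality using Kruskal-Wallis testing as well comparing the proportion of subjects with high IES scores", using Pearson's chi-square for the proportions. VAS (secondary objective 1) gets one Kruskal-Wallis test across the three modalities. Willingness to repeat and the top-ranked modality are only computed as proportions.

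The power statement takes high-IES rates of 1% for EGD ("Estimating that 1% of the subjects undergoing sedated EGD group"), 5% for Cytosponge ("5% of those undergoing Cytosponge") and 20% for TNE ("20% of those undergoing TNE will experience a high IES score"), "using a correlation of 0.3, and a sample size of 40". Then: "Random data were generated from such a distribution and Fishers Exact Test was computed from the data". The share of 10,000 simulated trials with p below 0.05 "provided our power estimate of 80% for a sample size of 40".

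The end of Section 9.1 adds analyses by recruitment pathway, a rule that non-significant tests are called inconclusive, and standard errors or confidence intervals for estimates. No section names a two-modality contrast, a post-hoc procedure or a multiplicity rule for the modality comparisons.

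**The concern.** A three-group test has one null hypothesis, that all three modalities are alike. Rejecting it supports only the statement that at least one differs. The useful questions are pairwise: does TNE differ in acceptability from EGD, does Cytosponge differ from EGD, and do the two alternatives differ from each other? If the plan is followed exactly, none of these is tested or estimated as a difference.

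Two things are at stake. A significant global p-value printed beside three medians or proportions invites a ranking that was never tested, and any pairwise tests added later would be chosen after the data were seen. In addition, the only power figure in the plan does not say which differences it covers, and under the plan's own rates the three pairs are in very different positions.

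**Working it through.** **Inputs (Section 9.1).** High-IES (>38) rates: EGD 1%, Cytosponge 5%, TNE 20%; 40 subjects, each with all three scores; two-sided 0.05; Fisher's exact test for power. Expected high scores out of 40: 0.4, 2 and 8.

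**Correlation.** The stated 0.3 cannot be a Pearson correlation between every pair of these binary outcomes. The maximum for rates p1 < p2 is √[p1(1−p2) / (p2(1−p1))]. For EGD and TNE this is √[(0.01 × 0.80) / (0.20 × 0.99)] = √0.0404 = 0.201. The paired calculations below therefore use correlations from 0 to 0.20.

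**Step 1: reproduce the 80%.** Enumerating a 3×2 Fisher (Freeman-Halton) test over three independent binomials with n=40 gives power **80.4%**. Simulations with correlated outcomes (latent normal correlation 0, 0.3, 0.6 and 0.9, and full nesting) give 80.3% to 81.9%; at latent 0.3 the figure is 80.8%. The stated figure is right as omnibus power.

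**Step 2: what drives it.** With TNE at 5% and the rest unchanged, the same enumeration gives **5.9%** (5.0% by simulation at latent 0.3).

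**Step 3: power for each pair.** For exact McNemar, the joint probability of two high scores is p1·p2 + ρ√[p1(1−p1)p2(1−p2)]. Subtracting it from each rate gives the two discordant probabilities, and power is summed over the discordant pairs in 40 subjects. Example, TNE vs EGD at ρ = 0.20: 0.002 + 0.20 × 0.0398 = 0.00996, so the discordant probabilities are 0.01 − 0.00996 = 0.00004 and 0.20 − 0.00996 = 0.19004; power 80%. At ρ = 0 they are 0.008 and 0.198; power 74%.

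| Pair (n=40, unadjusted 0.05) | Fisher | Exact McNemar, ρ 0 to 0.20 | Pearson, uncorrected |
|---|---|---|---|
| TNE vs EGD | 74% | 74–80% | 91% |
| Cytosponge vs TNE | 41% | 39–46% | 57% |
| Cytosponge vs EGD | 0.9% | 1.0–0.7% | 10% |

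Fisher and Pearson here treat the two columns as independent.

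**Hand check of the 0.9%.** With no high score on EGD and k on Cytosponge, the two-sided Fisher p is 2·C(40,k)/C(80,k): 0.055 at k=5 and 0.026 at k=6. So at least 6 of 40 are needed, where 2 are expected. P(0 on EGD) = 0.99^40 = 0.669 and P(6 or more on Cytosponge) = 0.0139. The product is 0.0093, which is nearly all of the 0.0095.

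**Step 4: what follows a significant global test.** In the simulation at latent correlation 0.3 the global Fisher test rejected in 0.8075 of trials. The fractions in which it rejected and the pair was also significant by Fisher were 0.7384 (TNE–EGD), 0.4067 (Cytosponge–TNE) and 0.0088 (Cytosponge–EGD). Dividing by 0.8075 gives 91%, 50% and 1%. A significant global result would usually come with a TNE–EGD separation, about half the time with a Cytosponge–TNE separation, and almost never with a Cytosponge–EGD one.

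**The case against.** Several points on the other side have weight.

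- A reader might infer that the 80% is really the power for TNE vs EGD. The figures do not support that. It is the omnibus figure, and the pair alone has 74% with the plan's own Fisher test, reaching 80% with exact McNemar only at the top of the correlation range. What holds is that the omnibus power is driven by the TNE assumption.
- A reader might also infer that the trial as a whole has about 1% power for Cytosponge vs EGD. That is too strong. The 1% belongs to Fisher or exact McNemar, whereas the planned test of proportions is Pearson's, which uncorrected gives about 10%. Both figures concern only the cut at 38. Section 9.1 also compares the IES score itself, and the documents give no score distribution from which its power could be computed.
- Section 9.1 already has safeguards. Calling non-significant tests inconclusive guards against reading a null result as equal acceptability, and standard errors or intervals will accompany estimates. This is partial mitigation: neither provides a between-modality difference, and the risk here lies in a significant global test.
- Section 3.1 asks only to assess each modality, which separate estimates could serve. But Sections 2 and 5.1 say the purpose is to compare.
- The power paragraph lists its three rates and its single test openly, so a careful reader can see that the 80% is a global figure. That readers would misapply it is a prediction.
- Pairwise follow-up is routine. Left unspecified, though, the contrasts, test and adjustment remain open until the data are in.

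**Conclusion.** The point stands in this form. The planned modality comparisons for IES and VAS are global only, so the plan as written can show that some modality differs but not which, and this falls short of the stated aim. The 80% is correct as omnibus Fisher power for the high-IES proportion (80.4%) and collapses to 5.9% if TNE is at 5%. For that dichotomy the pairs have about 74%, 41% and 1% power by Fisher; the last is about 10% by uncorrected Pearson, so Cytosponge and EGD cannot be expected to separate on the high/low outcome by any of these tests.

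Assumptions: the plan's rates; Fisher's test read as one 3×2 test per simulated trial; unadjusted pairwise levels; and all 40 subjects giving all three scores. Section 7.3.1 lets subjects who cannot swallow the Cytosponge continue, so Cytosponge contrasts may rest on fewer. The conclusion does not depend on how the 0.3 correlation is read. The change is worth making, but the global tests are not made useless by its absence.

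**What to change.** In Section 9.1:

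1. Name the three within-subject contrasts: TNE minus EGD, Cytosponge minus EGD, Cytosponge minus TNE. Report each as a paired difference with a 95% CI, for the IES score and for the high-IES proportion. A Hodges-Lehmann paired difference and a paired risk difference with an exact interval would serve; other paired estimators are equally acceptable. Name the same contrasts for VAS.
2. Prespecify one multiplicity rule. Either test pairs only after a significant global test that is valid for paired data (such as Friedman's test or Cochran's Q), or apply Holm to the three p-values without that gate. With three groups the gated route already controls the familywise error, so Holm on top of it is unnecessary.
3. Describe the 80% as power to detect any difference in the high-IES proportion, driven by the assumed 20% TNE rate. State that the high/low comparison cannot be expected to separate Cytosponge from EGD, so that its interval is what will be interpreted there.

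**Cost.** A few lines of text and code; no added patients, visits or data. The stated power becomes narrower in scope. Adjustment also costs pairwise power: at the Bonferroni level of 0.05/3, which Holm never falls below, simulated Fisher power at latent correlation 0.3 is 59% for TNE vs EGD, 25% for Cytosponge vs TNE and 0.2% for Cytosponge vs EGD.

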Since we are recruiting patients from two separate pathways (described in Section 5.1), we plan to account for the differences by analyzing the two groups separately as well as the entire cohort as a whole to see if there is a statistically significant difference in results between the groups. In addition, we acknowledge that the results may be affected by carryover effect for subjects recruited via Pathway 1, but recruiting via this strategy makes this study feasible, and we will acknowledge this as one of the limitations.

All hypothesis tests that are deemed to be not statistically significant will be reported as being inconclusive.

All statistical estimates of population parameters will be tabulated along with corresponding standard errors, or confidence intervals (CI) to convey levels of precision and imprecision.

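### Section 9.1 puts two unranked tests on the primary IES outcome, repeated by cohort, while the 80% power covers only the high/low comparison; one primary test, valid for paired data, should be named

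*Combined protocol and SAP*

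**What the plan says.** Section 3.1 sets the primary objective as patient acceptance measured by the IES score about seven days after EGD. Section 7.4.1 makes the IES the primary acceptability measure. Neither names a summary statistic or a test.

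Section 9.1 supplies the analysis: "We will compare the median IES score for each modality using Kruskal-Wallis testing as well comparing the proportion of subjects with high IES scores", the proportions by Pearson's chi-square. A high score is a total above 38. Acceptability is to be assessed with the IES scores "and the intrusiveness and avoidance subscales", but no test is named for the subscales.

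Because subjects come through two recruitment pathways, the end of section 9.1 adds "analyzing the two groups separately as well as the entire cohort as a whole". The stated aim is to see whether results differ significantly between the groups.

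The sample size rests on the high/low split alone. The rates are "Estimating that 1% of the subjects undergoing sedated EGD group, 5% of those undergoing Cytosponge" "and 20% of those undergoing TNE will experience a high IES score, using a correlation of 0.3, and a sample size of 40". The criterion is the share of simulated trials "in which the Fishers Exact Test p-value was less than 0.05", which "provided our power estimate of 80% for a sample size of 40". The value 0.05 appears only there; no significance level is given for the analyses themselves. No adjustment for multiple testing is described.

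**The concern.** One primary objective has two tests that ask different questions. The rank test responds to shifts anywhere in the score distribution; the chi-square responds only to crossing 38. They can easily disagree. TNE could raise scores modestly with few subjects above 38, or produce a few very high scores while the bulk of the distribution barely moves. The plan does not say which result would then be the trial's answer, and only one of the two comparisons was sized.

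Repeating the analyses by cohort adds further places where a significant result could appear. A significant result in one cohort but not the other is also not a test of whether the cohorts differ. What is at stake is the false-positive rate for the primary objective and whether its conclusion is fixed before the data are seen.

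**Working it through.** **Inputs from section 9.1.** 40 subjects, each scored on three modalities ("We plan to recruit 40 subjects for the study"); high-score rates 1%, 5% and 20%; correlation 0.3; criterion p < 0.05.

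**Assumptions not in the documents.** A 20/20 cohort split; skewed integer subscale scores, each capped at 35, with the total as their sum; correlation between the subscales of 0.4 or 0.7; every test read at 0.05. The correlation of 0.3 is applied on an underlying normal scale. As a correlation between the binary outcomes it is unattainable for the 1% and 20% pair, where the maximum is √[(0.01 × 0.80)/(0.99 × 0.20)] = 0.20.

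**1. The plan's own figure.** Simulating three correlated binary outcomes per subject (20,000 trials) and applying Fisher's exact test to the 3 × 2 counts gives power of 80.1%, 80.8% and 81.9% at correlation 0, 0.3 and 0.6. The stated 80% reproduces. The planned Pearson test gives 82.5% at 0.3. Expected high scores are 40 × 0.01 = 0.4, 40 × 0.05 = 2 and 40 × 0.20 = 8.

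**2. Benchmark if tests were independent.** 1 − 0.95² = 9.75% for two tests; 1 − 0.95⁶ = 26.5% for two tests in three populations.

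**3. Why the tests as written fall below this.** Kruskal-Wallis treats the 120 scores as independent. With equal within-subject correlation ρ, its statistic behaves approximately as (1 − ρ) times a chi-square on 2 degrees of freedom. Its true size at nominal 5% is therefore about exp[−5.991/(2 × 0.7)] = 1.4% at ρ = 0.3. Simulation on the skewed, tied scores gives 1.8 to 1.9%. Pearson's chi-square is conservative for the same reason, at 2.8 to 2.9%.

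**4. Chance of at least one p < 0.05 with no true difference** (6,000 trials per row-and-subscale setting, common high-score rate about 8%, close to the plan's average (1 + 5 + 20)/3 = 8.7%):

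| Tests | ρ | Two tests, whole cohort | Two tests, three populations |
|---|---|---|---|
| Kruskal-Wallis and Pearson (as written) | 0 | 8.4–9.0% | 18.4–19.0% |
| | 0.3 | 4.4–4.6% | 10.2–10.3% |
| | 0.5 | 2.2–2.6% | about 5.5% |
| Friedman and Cochran's Q (paired) | 0 to 0.5 | 8.9–9.2% | 18.6–19.9% |

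The ranges span the two subscale correlations. Repeat runs reached about 11% for the tests as written at 0.3 over three populations. For the paired tests they reached about 10% (two tests) and 21% (three populations).

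**5. Effect of naming one paired primary test.** For the high/low outcome at ρ = 0.3 (40,000 trials), Cochran's Q has a false-positive rate of 4.8% and power of 85.9% at the plan's rates. Pearson's test has 3.0% and 82.7%. One cohort of an assumed 20 has about 36% power by Fisher or 45% by Pearson.

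**The case against.** The strongest reply is that the tests as written do not inflate the error rate in the whole cohort. At the plan's own correlation the pair runs at about 4.5%, under the nominal level. That is correct, but it is no safeguard. It arises only because both tests ignore a pairing that section 9.1 itself expects, and it disappears once the tests are made valid for the design.

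Second, section 9.1 introduces the low/high classification as serving its planned analysis and sizes the study on it, so a primary is implied. That stands as a pointer, and it supports the fix. But the analysis paragraph lists the score comparison first and ranks neither, and section 3.1 speaks of the score.

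Third, the cohort analyses are framed as a check for differences between pathways, and section 5.1 makes Cohort B contingent on slow recruitment to Cohort A. Both points stand. The three-population figures apply only if both cohorts are filled and a single-cohort result is allowed to support a claim.

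A reader might infer something stronger: that up to 12 tests (two on the total and two on subscales, in three populations) are all read at 0.05, with a false-positive rate near 30%. The documents do not support that. No subscale test is named, no analysis significance level is stated, and the cohort analyses are not presented as separate routes to a claim. At correlation 0.3, figures of about 30% come from paired tests the plan does not name; as written, all 12 tests would give 13 to 15%.

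Finally, section 9.1 already promises standard errors or confidence intervals and reports non-significant tests as inconclusive. That meets part of the remedy, but does not say which test answers the objective.

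**Conclusion.** The point holds as a missing hierarchy. Two unranked tests address one primary outcome, there is no rule for disagreement, and the power statement covers only one of them. It does not hold as a claim that the two tests as written run well above 5% in the whole cohort: at correlation 0.3 they run at about 4.5%. The rate is about 10 to 11% if single-cohort results count. With paired tests it is about 9 to 10% in the whole cohort and 19 to 21% over three populations.

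These figures rest on an assumed score shape, reading each test at 0.05, equal correlation between modalities and, where cohorts enter, a 20/20 split. Equal correlation is least certain in Cohort A, whose Cytosponge IES comes from the prior study. The gap in interpretation depends on none of these assumptions.

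**What to change.** In section 9.1:

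- Name one primary test: the whole-cohort comparison across modalities of the proportion with IES above 38, by a repeated-measures test such as Cochran's Q. State its significance level; the sizing used 0.05.
- Restate power for that test. Under the plan's inputs it is about 86%, so 40 subjects still suffice. Splitting 0.05 equally between the two comparisons would instead leave about 69% (Fisher) or 73% (Pearson) for the high/low outcome.
- Make the total-score comparison the key secondary, by a paired test such as Friedman.
- Label subscale and separate-cohort results supportive, given as estimates with confidence intervals. Present any cohort contrast as a difference with its interval, not as two p-values side by side.
- Both paired tests need all three scores per subject. State how a subject without a Cytosponge score is handled, for example after the swallowing failure described in section 7.3.1.

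The cost is wording and one power calculation; no extra subjects or data are needed. The downside is that a significant score, subscale or single-cohort result can no longer be presented as the primary finding. The primary result will also rest on few high scores, about 10 expected in total (0.4 + 2 + 8). A sponsor who prefers the score as primary could choose it, but would then have to size the study on it.

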12.3 Impact of Events Scale (IES)

Below is a list of comments made by people in connection with their [Cytosponge/TNE/EGD] screening test. Please check each item, indicating how frequently these comments were true for you during the **past seven (7) days**. If they did not occur during that time, please mark the 'not at all' column.

	Not at all	Rarely	Sometimes	Often
I thought about it when I did not mean to.				
I avoided letting myself get upset when I thought about it or was reminded of it.				
I tried to remove it from my memory.				
I had trouble falling asleep or staying asleep, because of pictures or thoughts about it that came into my mind.				
I had waves of strong feelings about it.				
I had dreams about it.				
I stayed away from reminders of it.				
I felt as if it wasn't happening to me, or wasn't real.				
I tried not to talk about it.				
Pictures about it popped into my mind.				
Other things kept making me think about it.				
I was aware that I still had a lot of feelings about it, but I didn't deal with them.				
I tried not to think about it.				
Any reminder brought back feelings about it.				

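### Section 9.1 names medians as what Kruskal-Wallis compares for IES and VAS, but a rank test compares score distributions, and the plan defines no between-modality effect size for the scores

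*Combined protocol and SAP*

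**What the plan says.** The combined protocol and SAP, section 9.1, gives two analyses of the primary IES outcome in one sentence. The first is "We will compare the median IES score for each modality using Kruskal-Wallis testing". The second is "comparing the proportion of subjects with high IES scores for each modality using Pearson's chi-square testing", where "High score will be defined as total IES score >38". The section also names the intrusiveness and avoidance subscales, but gives neither a cut-off nor a separate analysis for them.

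For secondary objective 1 there is one analysis only: "Median VAS score will be compared between the three modalities using Kruskal-Wallis testing".

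The sample size in the same section rests on the high-score proportions: "Estimating that 1% of the subjects undergoing sedated EGD group, 5% of those undergoing Cytosponge" and "20% of those undergoing TNE will experience a high IES score", "using a correlation of 0.3, and a sample size of 40". The section says that each subject's scores will be correlated. Its closing paragraph asks for standard errors or confidence intervals with every estimate, but defines no difference between modalities for the scores.

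On the IES form in section 12.3 the lowest response is for comments that did not apply: "If they did not occur during that time, please mark the 'not at all' column". Item scoring and the expected share of subjects at the lowest score are not given.

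**The concern.** The plan names the median as the quantity compared. Kruskal-Wallis works on rank sums and asks whether scores on one modality tend to be higher than on another. The two questions coincide when the distributions share a shape and differ only by a shift. The plan neither states that condition nor makes it obviously plausible. IES is bounded below, and the planning rates have the modalities differing in the share of scores above 38.

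If most subjects report no distress after any procedure, all three medians sit at the floor while the distributions differ. A small p-value placed beside three equal medians would then be labelled a comparison of medians, and the score analysis would give no size for what was found. Replacing Kruskal-Wallis with Friedman to respect the pairing would not cure this, because Friedman is not a test of medians either.

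**Working it through.** **1. The plan's own figure.** Inputs from section 9.1: N = 40, high-score rates 1%, 5% and 20%, correlation 0.3, alpha 0.05, Fisher's exact test. Simulation of 10,000 trials gave 80.3% power with independent outcomes and 81.3% with a latent correlation of 0.3, against 80% stated. It reproduces. It concerns the high-score proportion, not the median comparison.

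**2. Equal medians with a significant Kruskal-Wallis: worked example.** Take 40 scores per modality (invented data):

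| | score 0 | score 5 | score 45 | median | share >38 | mean |
|---|---|---|---|---|---|---|
| EGD | 34 | 6 | 0 | 0 | 0% | 0.75 |
| Cytosponge | 30 | 8 | 2 | 0 | 5% | 3.25 |
| TNE | 24 | 8 | 8 | 0 | 20% | 10 |

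- Mid-ranks: the 88 zeros take 44.5, the 22 fives take 99.5, and the 10 scores of 45 take 115.5.
- Rank sums: EGD 34×44.5 + 6×99.5 = 2110. Cytosponge 30×44.5 + 8×99.5 + 2×115.5 = 2362. TNE 24×44.5 + 8×99.5 + 8×115.5 = 2788. Total 7260 = 120×121/2.
- Uncorrected H = [12/(120×121)] × (2110² + 2362² + 2788²)/40 − 3×121 = 4.853.
- Tie correction = 1 − (681,384 + 10,626 + 990)/1,727,880 = 0.5989.
- H = 4.853/0.5989 = 8.10 on 2 df, p = exp(−8.10/2) = 0.017.

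All medians are 0 and the test rejects. The planned proportions above 38 do show the difference here.

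**3. How often.** Assumptions beyond section 9.1: Gaussian copula with correlation 0.3; a mass at zero; other low scores uniform on 1–38; high scores uniform on 39–70. The zero shares and the 0–70 range are assumptions. High-score rates are 1/5/20%. There were 3,000 to 4,000 trials per scenario, and ranges come from repeated runs.

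| Share at zero, EGD/Cytosponge/TNE | Kruskal-Wallis p<0.05 | p<0.05 with three equal sample medians |
|---|---|---|
| 60/60/60% | 5–6% | 1% |
| 70/65/60% | 18–19% | 9% |
| 80/70/60% | 51–52% | 38–39% |
| 85/75/60% | 72–73% | 58–61% |
| 40/30/20% | not needed here | 0% |

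A more extreme 90/75/60% gave 88% and 75%. At 80/70/60% Friedman rejected in 62%, so it behaves in the same way.

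The true mean under this model is (1 − zero share − high share)×19.5 + high share×54.5. At 80/70/60% this is 0.19×19.5 + 0.01×54.5 = 4.25 for EGD and 0.20×19.5 + 0.20×54.5 = 14.8 for TNE. The difference is 10.55 points while both medians are 0.

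**4. Does the planned high-score proportion catch it?** Over the first four rows, p<0.05 with medians 0/0/0 and a non-significant chi-square occurred in only 0–8% of trials. With 85/75/60% at zero but closer high-score rates, it occurred in 36–42% of trials (1/5/10% or 5/5/5%). Under 5/5/5% the true mean TNE−EGD difference is (0.35 − 0.10)×19.5 = 4.9 points.

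**5. Identical distributions (60% at zero, 5% high in each).** Kruskal-Wallis rejected in 5.0%, 2.4% and 0.7% of trials at correlation 0, 0.3 and 0.5. Friedman rejected in 5.0%, 5.5% and 4.5%.

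**The case against.** The strongest reply is that the quoted sentence does not stop at the median. It goes on to the proportion above 38, on which the study is powered. In the 80/70/60% scenario, among trials with medians 0/0/0 and p<0.05, the chi-square was also significant in 90%, and the TNE and EGD proportions differed by at least 10 percentage points in 99%. That stands. A reader might infer that the plan's summaries hide the difference in total IES; under the plan's own rates they do not.

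Second, the floor is assumed. The planning rates say only that 99%, 95% and 80% of scores are 38 or below, and having a lowest response option does not show that most subjects use it throughout. That also stands, and the size of the effect depends on it.

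Third, a reader might see the rejection rates in the table as inflated type I error. They are not. In every row the modalities truly differ, and the test detects that. Under identical distributions Kruskal-Wallis rejects too rarely once scores are correlated.

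Fourth, VAS was not simulated, and nothing in the documents shows VAS scores piling up at no pain. For VAS the point is that no second summary is planned, not that a floor has been shown.

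What the reply leaves standing is the mismatch between hypothesis and test, the lack of a second summary with a stated cut-off for VAS and the subscales, and the dependence of total IES on the assumed rates.

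**Conclusion.** The concern holds as a modest point. Section 9.1 attaches a claim about medians to a test of distributions without the shape condition that would link them, and defines no between-modality effect size for the scores. Whether this matters in practice depends on an undocumented floor. With more than half of subjects at zero on every modality, rejection with equal sample medians ran from about 1% to 61% of trials over the four main scenarios. With zero shares of 40/30/20% it did not occur.

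For total IES the high-score proportion is an adequate companion if the 1/5/20% rates are about right, and a weaker one if they are closer together. VAS and the subscales have no such companion. The documents do not support the stronger readings: that false positives are inflated, that the primary result would be concealed, or that floor scores are expected. The 80% power figure is unaffected.

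**What to change.** In section 9.1, for IES, its subscales and VAS:

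- State that the scores will be compared with a within-subject rank test (for example Friedman, since the section says the scores are correlated), that it compares score distributions, and that its p-value supports no conclusion about medians.
- For each pair of modalities, report the within-subject mean difference with a 95% bootstrap interval, resampling subjects. Add the proportion of subjects scoring higher on one modality than on the other, with ties counted half.
- Keep medians and quartiles as description, and keep the planned high-IES proportions.

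The cost is a few sentences and a few lines of code. No new data, visits or subjects are needed. The downside is a little more analysis, and a mean difference on a skewed score needs a bootstrap interval. Other summaries, such as the share at zero, would also meet the reporting gap; what matters is to name one in advance.
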